**EFFECTS OF LOWER LIMB INTENSIVE FUNCTIONAL TRAINING ON
GAIT AND BALANCE IN SPASTIC DIPLEGIC CEREBRAL PALSY
CHILDREN**

NCT NO: None

Document Date: January 10,2023

Study Protocol:

Objective:

1. To compare outcomes of lower limb intensive functional training (LIFT) with conventional physical therapy on gait and balance in spastic diplegic cerebral palsy children.
2. To access if changes in motor capacity can further improve their motor performance level.

Study Design:

Randomized Controlled Trial

Study Method:

Settings

Children with Spastic diplegic from Physiotherapy Department of 2 different centers from Lahore.

Duration of Study

Duration of study was 9 months after approval of synopsis.

Sample Size

The calculated sample size using 30-sec chair test as outcome measure is 35 in each group after adding 20% dropout the sample size will be $35+7=42$ in each group.

$$n = \frac{2\sigma^2(z_{1-\alpha/2} + z_{1-\beta})^2}{(\mu_1 - \mu_2)^2}$$

$Z_{1-\alpha/2}$ Level of significance=95%

μ_1 Expected mean change in 30 sec chair rise test in Control group= 17.25

μ_2 Expected mean change in in 30 sec chair rise test in Experimental group= 13.25

δ_1 Expected standard deviation in Control group = 6.25

δ_2 Expected standard deviation in Experimental group = $5.12Z_{1-\beta}$

power of the study= 80%

n Expected sample size in a group= 35

After adding 20% drop out $35+7=42$ in each group.

Sampling Technique

Non-probability Purposive sampling technique was used.

Statistical Procedure:

SPSS version 21 was used for data entry and analysis. Quantitative variables presented with mean \pm SD and qualitative variables presented with frequency and percentage. Normality of the data was assessed with Shapiro-Wilk test. The data not fulfilled the assumption of normality. So, non-parametric test Friedman and Mann Whitney U test were applied. The p-value <0.05 was considered statistically significant

Group A: The Control group received conventional physical therapy (Stretching followed by Strengthening program and traditional gait training) at clinical setting. Stretching muscles were hip flexors, hip adductors, hamstrings and calf and stretching applied for 30 sec with 30 sec rest for 3 -5 times for each muscle group with in pain limit followed by strengthening exercise for weak muscle which includes the strengthening of anti-gravity muscles of lower limb they are: Quadriceps, Gluteus maximus and soleus performed in 3 groups. Each group contain 10 rep for each weak muscle group. Conventional Physical therapy applied 5 days/week for consecutive 20 weeks. They were also guided to perform activities at home but they're unbound to do the designed activities freely.

Group B: The experimental group will receive Lower extremity functional training (LIFT) at home environment and routine physical therapy at clinical setting. LIFT will be provided at home environment for 3 hours/day, 5days/week for 5 months. A log book will be maintained and the goals and strategies will be guided to child's parents. 3 hours' treatment will be performed in intervals at different time of the day. LIFT will help the child in motor learning, skill progression and resistance training to target the strength, proprioception and coordination impairments of the lower extremities. Motor learning will be based on Strength domain (Cycling) and progression from smooth to rough surface. Balance and Coordination domain involves activities such as (ball kicking with alternate legs and Static standing) and progression will be done by increasing accuracy and complexity. Proprioception domain (Vertical jumping, sit to stand and cursing) while applying knee-immobilizers if needed and progression number of repetitions and sets will be increased over time. Skill progression will be used to challenge the LIFT and make it intensive enough to obtain changes in motor skills and function. AFO's will be required during therapy session if needed.

Caregiver will be provided proper guidelines before implementing the treatment at home. 3 training sessions will be given prior to treatment. A log book will also be provided to get the structured record of the treatment. Further videos and mode of tele-rehabilitation will be used for supervision and guidance throughout the study. Therapist will closely monitor the activities by checking daily logs.

Data Analysis Procedure

Data will be analyzed using IBM SPSS version 21. The quantitative variables like age will be presented in the form of mean \pm SD and qualitative variables like gender will be presented in the form of frequency and percentage. After checking normality of data if parametric tests will be required the independent sample t-test will be used to determine mean difference of GMFM-88 for motor capacity and 6-min walk test, Timed Up and Go test and 30 sec chair raise test for motor performance. Further, mixed model will be used to compare the outcome variables at follow-ups on the other side if data will not be normally distributed then Friedman test will be used. P-value ≤ 0.05 will be considered as significant.

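### The two named two-sample tests cannot account for centre, which costs a little precision that is cheap to recover

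*Combined protocol and SAP*

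**What the plan says.** Under Study Method, Settings, children come from the "Physiotherapy Department of 2 different centers from Lahore". Study Design is given as "Randomized Controlled Trial". No allocation method is described, and nothing says whether arms were balanced within centre.

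Two sections describe the analysis:

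- **Statistical Procedure** says the data failed the normality assumption and continues: "So, non-parametric test Friedman and Mann Whitney U test were applied". Of these two, only Mann-Whitney compares the arms; Friedman compares time points within a group.
- **Data Analysis Procedure** covers the normal-data case: "the independent sample t-test will be used to determine mean difference of GMFM-88", and likewise for the walking, Timed Up and Go and chair-rise tests. A mixed model is added for follow-ups, without a list of its fixed or random terms.

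Centre is not mentioned in either section, and no by-centre or sensitivity analysis is planned.

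**The concern.** Centre could plausibly affect outcome. Both arms receive clinic-based therapy, the routine therapy in Group B is not described further, and sampling is purposive, so case mix may differ between the departments. If it does, part of the spread in the outcome is a difference between centres that the analysis could remove. A t-test or Mann-Whitney test leaves that part in the error term, so the interval for the treatment effect is wider, and the power lower, than the same children could give. Recruiting centre should be known for every child, so no new data are needed to recover it.

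**Working it through.** **Inputs from Sample Size.** Control mean: "chair rise test in Control group= 17.25". Experimental mean: "chair rise test in Experimental group= 13.25". The absolute difference is 4.00. The SDs are 6.25 and 5.12, alpha is 0.05 two-sided, power is 80%, and there are 35 per group, or 42 after the dropout allowance.

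**The plan's own figure.** Root-mean-square SD = sqrt((6.25² + 5.12²)/2) = 5.713. The plan's formula gives n = 2 × 5.713² × (1.960 + 0.842)² / 4² = 32.02, so 33 per group. The stated 35 is within 2 of this, so 5.713 is a reasonable planning SD.

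**Assumptions.** The documents do not give the centre difference or the split of children between centres. I take an even split and a centre difference of k = 0.3, 0.5 or 0.8 within-centre SDs.

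**Variance and interval width.** The share of outcome variance due to centre is f = (k²/4)/(1 + k²/4). Adjusting multiplies the interval width by sqrt(1 − f). With 42 per arm the unadjusted 95% half-width is 1.96 × 5.713 × sqrt(2/42) = 2.44 chair rises.

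| k | f | sqrt(1 − f) | Adjusted half-width | Narrower by |
|---|---|---|---|---|
| 0.3 | 2.2% | 0.989 | 2.42 | about 1% |
| 0.5 | 5.9% | 0.970 | 2.37 | about 3% |
| 0.8 | 13.8% | 0.929 | 2.27 | about 7% |

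These figures are before the small cost of estimating the centre effect, which matters most at k = 0.3, where there is little to gain.

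**Chance imbalance is the same benefit.** Under simple randomisation the difference in centre share between arms has standard error sqrt(0.25 × 2/42) = 0.109, and 1.96 × 0.109 = 0.214. At k = 0.5 the within-centre SD is 5.713 × 0.970 = 5.54, so an imbalance of that size shifts the estimate by 0.214 × 0.5 × 5.54 = 0.59 chair rises. Removing it from the unadjusted half-width in quadrature gives sqrt(2.44² − 0.59²) = 2.37, the figure already in the table. The shift is part of the existing interval and must not be added to the variance gain.

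**Power.** Here the centre difference g is in total-SD units, so the variance removed is g²/4, slightly more than f for the same number. By normal approximation at 35 per arm, power is 83.4% unadjusted. With adjustment it is 83.9% at g = 0.25, 85.7% at 0.5 and 88.5% at 0.75.

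**Behaviour of the rank tests.** These are simulated rejection rates: 4,000 runs, 35 per arm, normal outcomes, centres evenly split on average. Simulation error is about 0.3 points near 5% and 0.6 points near 80%.

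| Allocation | g | Type I error: Mann-Whitney / van Elteren | Power: Mann-Whitney / van Elteren |
|---|---|---|---|
| Simple | 0 | 5.5% / 5.8% | 81.2% / 80.2% |
| Simple | 0.5 | 5.2% / 5.0% | 79.8% / 81.8% |
| Simple | 1.0 | 4.7% / 4.8% | 79.8% / 89.2% |
| Within centre | 0.5 | 4.0% / 4.9% | 78.7% / 80.4% |
| Within centre | 1.0 | 1.9% / 5.1% | 83.4% / 89.8% |

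Mann-Whitney does not exceed its level by more than simulation error in either case. Under within-centre allocation it falls below 5%, because the design has removed a source of variation that the test still counts.

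**The case against.** The strongest reply is that an unadjusted two-sample test is valid here, and that with two centres adjustment is largely a matter of preference. Most of this stands. Under simple randomisation, chance differences in centre mix are ordinary sampling error already covered by the standard error. The size of any gain rests on a centre effect that the documents do not supply. It may be small: the main experimental component is delivered at home, and conventional therapy follows one written description of muscles, repetitions and frequency. If centre has no effect, stratifying gains nothing and may cost about one point of power (80.2% against 81.2%, which is near simulation error).

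The reply does not remove the point. A t-test or Mann-Whitney test cannot use centre, and the alternatives that can are almost free.

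Two stronger readings are tempting. A reader might infer that centre confounds the comparison or inflates false positives; the documents call the trial randomised, and the error rates above do not show inflation. A reader might also infer that every planned between-arm analysis leaves centre out. For the mixed model that is not shown: its terms are simply not listed.

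**Conclusion.** The point holds as a modest loss of precision. The documents name two centres and two two-sample tests that cannot account for them. On an assumed even split and a centre difference of 0.3 to 0.8 SD, the avoidable excess is about 2% to 14% of outcome variance, or about 1% to 7% of interval width. If allocation was stratified by centre, the unadjusted test is also conservative. Which allocation applied cannot be settled from the documents. The percentages depend on assumptions about centre, and the simulations use normal outcomes although Statistical Procedure reports non-normal data, so both show likely scale only. Severity is low.

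**What to change.** 1. For the between-arm comparison reported as applied, replace Mann-Whitney with the van Elteren test stratified by centre.
2. In the normal-data branch, replace the t-test with a linear model containing arm and centre, and list centre as a fixed effect in the mixed model. This step alone would not change the comparison reported as applied, so the first is the one that matters.
3. State whether allocation was stratified by centre.

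If outcome data have already been examined, as the past tense in Statistical Procedure suggests, report the stratified result beside the original one and label it as added later.

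The cost is a line or two of analysis text, one degree of freedom in the models, and up to about one point of power if centre has no effect.

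### A normality check on the trial's own data chooses the analysis, and its failing branch replaces the planned mixed model with a Friedman test that does not compare the arms

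*Combined protocol and SAP*

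**What the plan says.** Two sections of the combined protocol and SAP bear on this point.

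- **Data Analysis Procedure** (future tense) sets a conditional rule. The parametric branch reads "After checking normality of data if parametric tests will be required the independent sample t-test will be used to determine mean difference". For follow-up, "mixed model will be used to compare the outcome variables at follow-ups on the other side if data will not be normally distributed then Friedman" is the rule, so the mixed model gives way to the Friedman test if normality fails. The outcomes covered are "GMFM-88 for motor capacity and 6-min walk test, Timed Up and Go test and 30 sec chair raise test for motor performance", four in all.
- **Statistical Procedure** (past tense) reports that the check was made and failed: "Normality of the data was assessed with Shapiro-Wilk test. The data not fulfilled the assumption of normality". It continues: "So, non-parametric test Friedman and Mann Whitney U test were applied".

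The Friedman fallback is therefore written into the rule. Mann-Whitney U is not named in Data Analysis Procedure and appears only in the past-tense report. Neither section says which outcome, arm or visit is checked, whether raw values or residuals are used, or at what level. Neither says what happens if some outcomes pass and others fail.

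**The concern.** The first objective is to compare the two treatments on gait and balance. The analysis should therefore estimate a between-arm effect that is defined before the data are examined. Here a significance test on the data decides both the method and the quantity estimated: a mean difference in one branch, a rank comparison in the other.

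The sample size rests on a difference in means, which the rank tests do not estimate. The failing branch also loses the mixed model. Friedman asks whether measurements differ across visits within the same children. If both arms improve equally, it can be clearly significant while saying nothing about which treatment is better.

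Because the check is undefined and its result is given as one verdict, a reader cannot reproduce the decision that led to the reported tests.

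**Working it through.** **1. What the trial was sized on.** Inputs from Sample Size: means 17.25 (control) and 13.25 (experimental), SDs 6.25 and 5.12, "Level of significance=95"% (read as two-sided alpha 0.05 from the formula's subscript), "power of the study= 80"%, and 35 per group.

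- Difference in means: 17.25 − 13.25 = 4.00.
- Common SD: √((6.25² + 5.12²)/2) = √((39.06 + 26.21)/2) = 5.713.
- n = 2σ²(1.960 + 0.842)²/(μ₁ − μ₂)² = 2 × 32.64 × 7.849/16 = 32.02, rounded up to 33 per group. The t-based solution is 33.01, rounded up to 34.

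This is within two children of the stated 35. The formula contains only means and variances, so the planned effect is a difference in means.

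**2. Does a Shapiro-Wilk rejection show that the mean comparison fails?** The documents give no outcome distribution, so skewness is an assumption. Data were simulated at 35 per arm with SD 5.71 and a pure shift of 0 or 4. The ranges span repeated runs.

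| Assumed distribution | Shapiro-Wilk rejects in one arm | t-test power | Mann-Whitney U power |
|---|---|---|---|
| Normal | about 5% | 81–82% | 79–80% |
| Gamma, skewness 1 | 51–52% | 81–83% | 86–87% |
| Gamma, skewness 2 | 98–99% | 82% | 96–97% |

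The t-test's type I error was 4.6% to 5.4% across these runs. With skewed counts and lognormal data (coefficient of variation 0.5), at 35 or 42 per arm, it was 4.5% to 5.1%. So the t-test holds its level even where the check nearly always rejects.

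**3. Does the two-stage rule itself distort the error rate?** The rule simulated was Mann-Whitney U if either arm is rejected, otherwise the t-test. Its type I error was about 4.5% to 5.6% across all runs. There is no material inflation.

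**4. What each branch can answer about the first objective.**

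| | Between-arm comparison | Across visits |
|---|---|---|
| Passes normality | t-test (mean difference) | Mixed model, which can carry arm, visit and arm-by-visit |
| Fails normality | None named in Data Analysis Procedure; Mann-Whitney U reported in Statistical Procedure | Friedman: visits within children only |

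The failing branch has no test of whether change over follow-up differs between arms, and no estimate on the scale used in step 1.

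**The case against.** The strongest reply is that the rule was written down and followed, and that the rank tests cost nothing in error rate and may gain power. Most of that stands, and it rules out several stronger readings that a reader might infer.

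- **That the switch was unplanned.** The documents do not support this. The Friedman fallback is in Data Analysis Procedure; only Mann-Whitney U is not.
- **That rejection was likely, or an artefact of many checks.** With exactly normal data and independent checks, 4 outcomes × 2 arms at one time point gives at least one rejection with probability 1 − 0.95⁸ = 0.34. But a single check rejects only about 5% of the time. The plan states neither the number of visits nor a rule that any one rejection suffices. If most variables failed, chance is a poor explanation.
- **That chance decided which outcomes were modelled and which were ranked.** One overall verdict is reported, and no split between outcomes is documented.
- **That the rule inflates false positives or loses power.** It does neither to any material degree. Under a pure shift in skewed data Mann-Whitney U is the more powerful test, at 86% to 97%. Under normality it gives up about 2 points.
- **That no between-arm test remained.** Mann-Whitney U does compare the arms, although the plan does not say at which visits or on which values.

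What the reply does not answer is the change of estimand, the loss of the longitudinal between-arm model, and the undefined check.

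**Conclusion.** The point holds in a limited form and should be acted on. A data-dependent and undefined check moved the analysis away from the mean difference on which the trial was sized. It also removed the only planned method that could test arm and arm-by-visit effects over follow-up. A Shapiro-Wilk failure did not require this: at 35 per arm the t-test kept about 5% type I error and 81% to 83% power for the 4-rise difference.

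Those figures assume gamma skewness of 1 to 2, a pure shift, a common SD of 5.71 and 35 analysed per arm. The documents give neither the observed distributions nor the number of visits. The plan also does not list the mixed model's terms, so the conclusion reads it as able to include arm and arm-by-visit. The damage is to what is estimated and to reproducibility, not to the error rate.

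**What to change.** - Delete the normality check as a means of choosing the analysis.
- Use the mixed model already named in Data Analysis Procedure for all four outcomes, with arm, visit and arm-by-visit terms, whatever Shapiro-Wilk shows. Report the between-arm mean difference at each follow-up.
- Give a bootstrap or robust interval for every outcome. Using it only where residuals look skewed would bring back a choice made on the data.
- Report Mann-Whitney U between arms at each follow-up as a labelled sensitivity analysis.
- State that the re-run is post hoc, since the analysis is already described as done, and that the reported rank tests followed the normality check.

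The cost is revised SAP wording and one re-run on data already held, with no new children or visits. The downside is some loss of power against rank tests if an outcome is strongly skewed (82% against 96–97% at assumed skewness 2), which the sensitivity analysis covers.

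### The named two-group tests use no baseline covariate and the mixed model states no baseline term: the tests are valid, but some precision may be lost (minor)

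*Combined protocol and SAP*

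**What the plan says.** The Study Design section calls the study a "Randomized Controlled Trial". The analysis is described in two places.

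- **Statistical Procedure** (past tense): "The data not fulfilled the assumption of normality", and then "So, non-parametric test Friedman and Mann Whitney U test were applied".
- **Data Analysis Procedure** (future tense): if parametric tests are suitable, the "independent sample t-test will be used to determine mean difference of GMFM-88 for motor capacity and 6-min walk test", and likewise for Timed Up and Go and the 30-second chair test. A "mixed model will be used to compare the outcome variables at follow-ups" is added; otherwise, "if data will not be normally distributed then Friedman test will be used".

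Neither section names a covariate, ANCOVA or any other baseline term, and neither says whether the end score or the change from baseline is tested. The one hint is in the Sample Size section, where the planning input is labelled "Expected mean change in 30 sec chair rise test in Control group", with a matching label for the experimental arm.

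**The concern.** The first objective is to compare LIFT with conventional therapy, and only a two-group contrast answers it. The Mann-Whitney test and the t-test, as named, take no covariate. Friedman's test compares time points and gives no adjusted group contrast. The mixed model could use baseline, either as a covariate or as one of the repeated measures, but no such term is stated. It also belongs to the parametric branch, which the Statistical Procedure section indicates was not followed.

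A baseline measurement seems to exist. This is an inference from the change label in the sample size, the mention of follow-ups and the use of Friedman's test, since no assessment schedule is given. If it exists, it usually explains part of the variation in the end score. With about 33 to 35 evaluable children per group, using it could sharpen the comparison without new data. If end scores were tested, a chance imbalance at baseline would also go unaccounted for.

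**Working it through.** **Inputs from the Sample Size section.** Means 17.25 and 13.25 (absolute difference 4), SDs 6.25 and 5.12, two-sided α 0.05, power 80%, 35 per group, 42 after the dropout allowance.

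**Assumed.** Rho, the baseline-to-end correlation, is not in the documents; the range taken is 0.2 to 0.9. Data are normal, with equal SDs at baseline and end.

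**1. The plan's own figure.**
- SD = √((6.25² + 5.12²)/2) = 5.713.
- n = 2 × 5.713² × (1.960 + 0.842)² / 4² = 32.02, rounded up to 33 per group. The stated 35 covers this.

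**2. Unadjusted power.** 42 less 20% is 33.6, so 33 per group. The standardised difference is d = 4/5.713 = 0.700.
- t-test at 33: noncentrality 0.700 × √(33/2) = 2.844, df 64, power 80.0%. At 35 per group: 82.3%.
- Mann-Whitney at 33, simulated: about 78%.

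**3. What adjustment does to the variance.** With σ the SD of a single score, the variances are σ² (end score), 2(1 − rho)σ² (change) and (1 − rho²)σ² (adjusted for baseline).
- If 5.713 is the SD of end scores, adjustment multiplies the variance by 1 − rho².
- If 5.713 is the SD of change, the factor is (1 − rho²)/(2(1 − rho)) = (1 + rho)/2.

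The adjusted noncentrality is 2.844/√factor, with df 63. At rho 0.5 both factors are 0.75, so it is 2.844/√0.75 = 3.284 and power is 89.9%.

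**4. Power at 33 per group.** ANCOVA is by noncentral t, to be compared with the t-test's 80.0%. The rank test is a Mann-Whitney test on residuals from regressing the end score on baseline, to be compared with about 78%. It was simulated with 20,000 runs per cell.

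| rho | ANCOVA, end score | Rank test, end score | ANCOVA, change | Rank test, change |
|---|---|---|---|---|
| 0.2 | 81.5% | 79% | 95.1% | 94% |
| 0.3 | 83.5% | 81% | 93.5% | 92% |
| 0.5 | 89.9% | 88% | 89.9% | 88% |
| 0.7 | 97.5% | 96% | 85.9% | 84% |
| 0.8 | 99.7% | 99% | 83.9% | 81% |
| 0.9 | 100% | 100% | 81.9% | 79% |

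A separate run of 4,000 per cell put the last rank-test entry at 80%. The two readings move in opposite directions with rho: the gain is smallest at low rho for end scores and at high rho for change.

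**5. Validity.** With zero effect, at rho 0.2, 0.6 and 0.9 and for normal and lognormal data, all simulated rejection rates were 4.5% to 5.2%, adjusted and unadjusted alike.

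**6. A skewed example.** With lognormal data (log-SD 0.6), the adjusted rank test gave 95% to 100% against 95% for end scores, and 94% to 99% against 91% to 93% for change.

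**7. Which slope to use for the estimate.** Suppose the end score is regressed on baseline without group, and the groups differ at baseline by δ SDs. The residual shift then estimates the true effect divided by (1 + δ²/4). At δ = 0.5 this is 4/1.0625 = 3.76. In simulation the average estimate was about 3.92 to 3.97 for a true 4, and about 3.6 to 3.9 when the imbalance exceeded 0.4 SD. With the slope fitted with group in the model, the average was 3.98 to 4.03.

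**The case against.** The strongest reply is that nothing here is wrong. The tests are valid, the sample size reaches 80% by t-test without adjustment, and the benefit cannot be stated because rho, the tested value and the assessment schedule are all missing. The only textual clue, the change label in the sample size, suggests that baseline may already be used by subtraction. In that case the gain at high rho is small: about 4 points at 0.8 (77.3% to 81.0%) and 1 to 2 points at 0.9. The mixed model may also contain baseline, since a term unlisted in a one-sentence plan is not shown to be absent. And the analysis is reported in the past tense, so little can change.

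Most of this stands, and it is why the point is minor. It does not remove the point. Subtraction is only partial use of baseline, and covariate adjustment is at least as precise in large samples. The mixed model belongs to the branch not followed. Stating the tested value costs nothing whatever rho is.

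A reader might go further and infer that leaving baseline out biases the comparison or makes the trial underpowered. The documents do not support either reading. The allocation is described as randomised, the simulated type I error is about 5%, and the 78% for Mann-Whitney is a normal-data figure at the lowest expected number of evaluable children. That figure does not carry over directly to data reported as non-normal.

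**Conclusion.** The point holds as a minor efficiency improvement. The named two-group tests use no baseline covariate, and no baseline term is stated for the mixed model. Precision may therefore be lost, by an amount the documents do not let anyone determine. For assumed rho of 0.2 to 0.9, the possible gain for the rank test runs from about 1 point to over 20 (end score), or from about 16 points down to 1 or 2 (change).

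These figures rest on normal data, equal SDs, one follow-up and an inferred baseline measurement. Because the Statistical Procedure section reports non-normality, they are only a guide. Bounded or heavily tied scores were not simulated. The sample size and the validity of the Mann-Whitney result are not in question.

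**What to change.** 1. State whether the end score or the change is the tested value, for each outcome.
2. Where normality holds, use ANCOVA of the end score on group and baseline of the same outcome, or the planned mixed model with a stated baseline covariate. Report the adjusted difference with its 95% CI.
3. Where normality fails, which is the branch reported, add a Mann-Whitney test on residuals from regressing the end score on baseline. For the p-value the regression is pooled over groups.
4. For the effect, report the Hodges-Lehmann shift of end score minus slope × baseline, with the slope estimated with group in the model. Give a bootstrap 95% CI that resamples within group and refits the slope each time. A slope fitted without group pulls the estimate toward zero when the groups differ at baseline.
5. If the outcome data have already been analysed, as the Statistical Procedure section indicates, report this beside the Mann-Whitney result, labelled post hoc and supportive. It should not replace that result.

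**Cost.** No new data if baseline was recorded; one extra analysis per outcome and one degree of freedom. The test and the interval use slightly different slopes, which should be stated, and the coverage of this form of the interval was not simulated. The gain may be small if rho is low (end score) or high (change).

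### Objective 1 is worded as LIFT versus conventional therapy, but no arm receives LIFT without clinic therapy; the objective and conclusion should be limited to the contrast that the two arms test

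*Combined protocol and SAP*

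**What the plan says.** The Objective section gives the first aim as: "To compare outcomes of lower limb intensive functional training (LIFT) with conventional physical therapy on gait and balance in spastic diplegic cerebral palsy children". Neither that section, Statistical Procedure nor Data Analysis Procedure describes LIFT as given in addition to other therapy.

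The arms are set out in the Group A and Group B paragraphs.

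- Group A, clinic: "The Control group received conventional physical therapy (Stretching followed by Strengthening program and traditional gait training) at clinical setting". The schedule follows: "Conventional Physical therapy applied 5 days/week for consecutive 20 weeks".
- Group A, home: "They were also guided to perform activities at home but they're unbound to do the designed activities freely". The text does not say what these activities were, how much was done, or whether they were recorded.
- Group B, both components: "The experimental group will receive Lower extremity functional training (LIFT) at home environment and routine physical therapy at clinical setting".
- Group B, amount of the home part: "LIFT will be provided at home environment for 3 hours/day, 5days/week for 5 months".

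The Group B text also gives the home programme a support structure: three caregiver training sessions beforehand, a log book that the therapist checks daily, and videos and tele-rehabilitation for supervision. It says nothing more about the clinic part beyond calling it routine.

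**The concern.** As worded, Objective 1 treats LIFT and conventional therapy as alternatives. Group B receives clinic therapy as well as LIFT, so the arms do not test that question. A favourable result reported in the words of the objective could be taken to mean that LIFT outperforms conventional therapy, or that a family could do LIFT at home in its place. Neither arm provides evidence for that. What is at stake is the meaning of the main conclusion. The randomisation, outcomes, tests and sample size are not affected.

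**Working it through.** The plan gives no figure on this point to reproduce. The 35 per group in the Sample Size section rests on a mean and SD for each group and does not depend on how the contrast is named. The check is therefore a comparison of texts.

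**Step 1. The arms side by side.**

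| | Group A | Group B |
|---|---|---|
| Clinic therapy: name | conventional | routine |
| Clinic therapy: content | stretching, strengthening, traditional gait training | not stated |
| Clinic therapy: schedule | 5 days a week, 20 weeks | not stated |
| Home component | guided, free to do or not | LIFT, 3 hours a day, 5 days a week, 5 months |
| Support for home component | none described | caregiver training, log book, videos, tele-rehabilitation |

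Arms with LIFT and no clinic therapy: 0 of 2.

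**Step 2. What the comparison identifies.** Write C_A and C_B for the clinic therapy in each group, H for Group A's unstructured home activity, and L for the whole home LIFT programme. Suppose, for illustration only, that the effects add.

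- Group A = C_A + H
- Group B = C_B + L
- Difference B − A = (C_B − C_A) + (L − H)
- Objective 1 as worded asks about L − C_A

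If C_B = C_A, the difference reduces to L − H. It is positive whenever L exceeds H, whether L is larger or smaller than C_A. So even with identical clinic therapy the result says nothing about LIFT against conventional therapy. If the effects do not add, L against H is known only in children who also have clinic therapy, and the conclusion is the same.

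If C_B differs from C_A, the two brackets cannot be separated, and the result compares two packages.

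**Step 3. What L and H contain.** L is more than the exercises. It includes the prescribed hours, caregiver training, log book and remote supervision. H is not zero by design, because Group A was guided in home activities. The difference is therefore a structured, supervised home programme against unstructured home activity, not the exercises against nothing.

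**Step 4. Amounts that can be stated.**

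- Prescribed LIFT: 3 × 5 = 15 hours a week. Over 20 weeks: 15 × 20 = 300 hours. Over five calendar months: 15 × 5 × 52/12 = 325 hours.
- Group A clinic sessions: 5 × 20 = 100.
- Group B clinic sessions, clinic session length in either group, and Group A home time: not stated.

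A net difference in practice time cannot be calculated from these.

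**The case against.** The strongest reply is that an objective is a one-line label naming the experimental ingredient and the comparator, and that the Group B paragraph discloses the clinic component in its opening sentence. A reader of both sections sees what was compared. The documents contain no conclusion, so the harm is only prospective. This stands as a limit on severity. It does not remove the mismatch, because the conclusion is expected to answer the objective, and the objective as worded is not what the arms test.

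A second reply is that *routine* plainly refers back to the programme described just before it. Both therapies are placed at the clinic, and 20 weeks and five months are roughly the same period. This is the natural reading, and the undescribed clinic part would by itself be only missing detail. But it leaves the main point untouched, since Step 2 holds with identical clinic therapy.

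A reader might infer more than the documents support:

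- *That the design is faulty or needs a LIFT-only arm.* Giving LIFT alongside clinic therapy is a legitimate design. Only the stated question fails to match it.
- *That clinic therapy differed between the groups.* Nothing says so. The text uses two different words without linking them.
- *That equal clinic therapy would give a clean add-on effect of LIFT.* Group A's home activities and the support bundled with LIFT prevent that.
- *That Group B practised 15 hours a week more than Group A.* Fifteen hours is the prescribed LIFT time, not a net difference.

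**Conclusion.** The point holds as a mismatch between objective and conclusion on one side and the arms on the other. With 0 of 2 arms receiving LIFT without clinic therapy, the trial cannot support a statement that LIFT is better than, or can replace, conventional therapy. This rests on the arm descriptions alone and needs no assumption about the clinic programmes.

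What the trial can support depends on one unwritten fact. If clinic therapy was the same in both groups, it compares the whole home LIFT programme with unstructured home activity, both alongside clinic therapy. If it was not, it compares two packages. Severity is minor to moderate: the validity of the between-group comparison is unaffected, but its interpretation depends on the correction.

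**What to change.** Keep Objective 1 on record as it stands and add a dated clarification. Limit the objective and the conclusion to: *a structured, supervised home LIFT programme plus clinic physical therapy versus clinic physical therapy with unstructured home activities*, with no claim that LIFT replaces conventional therapy.

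The clarification should say whether it was made before or after analysis. The documents are mixed on this: Statistical Procedure reports "So, non-parametric test Friedman and Mann Whitney U test were applied", while Data Analysis Procedure is written in the future tense. A silent edit of the objective would not be acceptable if results were already known.

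Reconcile *routine* in the Group B paragraph with *conventional* in the Group A paragraph by stating whether the two clinic programmes were the same. If they were not, describe what Group B received and report the result as a comparison of two packages.

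The cost is a short clarification and a narrower claim. No patients, visits or procedures are added, and the endpoints, tests and sample size stay as they are.
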